Subjects who respond will be given a thorough review of the risks, discomforts, potential benefits to the study and their expected involvement using a prepared script approved by our Institutional Review Board. Subjects will be given a copy of the informed consent and allowed a minimum of 24 hours to review the information and make a decision on study participation. During this time, the subject will have the opportunity to discuss the research with his/her primary care physician or clinician. The study investigators will be available to answer any questions should any arise. Informed consent will be obtained by the Principal Investigator or an experienced co-investigator prior to participation in the study. The opportunity to talk to a licensed MD (who is readily available at the time of consent, and available overnight at the hospital) will be offered in each case. Subjects will have more than 24 hours to consider participating in the study. Any consent issues / problems will be reported to the PHRC in real time rather than waiting to report at the time of Continuing Review

Inclusion and exclusion criteria will be carefully assessed prior to enrollment. Assuming subjects meet the inclusion criteria, they will begin the protocol by scheduling their overnight studies in the clinical/physiology laboratories. Subjects will be informed that they may withdraw from the study at any point, with no impact on their ongoing care. We have not previously had difficulty enrolling participants into similar studies performed in our laboratory.

If the data collected will be considered insufficient by the PI or by the co-investigators, the subject will be asked to repeat the whole study or a part of it without signing a new informed consent form.

After completing the main study, patients enrolled will be asked to perform two extra study nights in which atomoxetine and oxybutynin alone will be administered if they showed an improvement in EMG_{GG} activity and OSA severity in the night in which they took the combined therapy.

V. STUDY PROCEDURES

The effect of Atomoxetine and Oxybutynin on OSA severity and genioglossus muscle activity (EMG_{GG})

Protocol:

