Two overnight sleep studies will be performed approximately 1 week apart: a placebo night and a Atomoxetine-Oxybutynin (ato-oxy, 80-5 mg PO) night, in double-blinded randomized control design. For each night, the subjects will arrive at the sleep laboratory at approximately 7:00pm. A physician will complete a complete physical and medical history. The placebo or ato-oxy will be administered 30 minutes before lights out. At least 15 minutes of quiet wakefulness will be recorded to quantify the subject's awake EMG_{GG} activity. Subjects will then be allowed to fall asleep during which we will assess EMG_{GG} activity throughout the rest of the evening (see below for details).

DETAILED PROTOCOL (version approved 6/26/2017)

Measurements and equipment:

Subjects will be instrumented with standard polysomnography (PSG) recording sensors. Sleep stage and arousals will be measured with electrodes pasted on to the scalp, face, chin and chest (EEG, EOG, EKG, chin EMG). Paste-on EMG electrodes will be placed over the anterior tibialis muscle to detect leg movements. Respiratory effort belts will be placed around the chest and abdomen to measure breathing movements. Oxygen saturation will be measured continuously with a pulse oximetry probe placed on either the fingertip or earlobe. Snoring will be detected with a small microphone positioned over the suprasternal notch. Body position will be recorded with a sensor taped to the thoracic belt. Each of these devices is standard for diagnostic PSG and should not be uncomfortable.

One nostril and the back of the throat will be anesthetized with 4% lidocaine; only 2–3 ml (80–120 mg) of lidocaine is used. One small, flexible pressure-tipped catheter (Millar) will then be inserted through the anesthetized nostril until the tip of the catheter is located just above the epiglottis (or in the esophagus) by visual inspection through the mouth. This catheter is used to assess upper airway negative pressure and to calculate airflow resistance both awake and during sleep. In case of an esophageal catheter, after the visual inspection of the mouth, the patient will be required to swallow several times and the catheter will be advanced slowly to the lower third of the esophagus.

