Sleep stages, arousals and respiratory events will be scored by a registered polysomnographic technologist blinded to the treatment allocation according to the American Academy of Sleep Medicine recommended criteria.

Muscle activity will be quantified using standard procedures described in our previous studies (1, 23, 24). Briefly, the raw EMG_{GG} signal will be rectified and smoothed with a 100 msec window. The peak phasic, as well as tonic, activity of the smoothed signal will be identified for each breath. Data from quiet wakefulness (free of swallowing and movement artifacts) will be averaged to determine the peak phasic and tonic activities during this state. The same will be done for stable NREM and REM sleep (free of arousals and other artifacts). Pharyngeal muscle responsiveness will be determined by calculating the slope and intercept of the esophageal pressure versus muscle EMG relationship.

Reimbursement

Subjects will receive \$100/night for participation in each overnight study (TOTAL = \$200). Reimbursement for parking expenses will be provided.

If the subjects will repeat a part or the entire protocol because of insufficient data collection, they will be reimbursed \$100 for any extra night.

If the subjects will take part to the additional nights on atomoxetine and oxybutynin alone, they will be paid \$100/night (total \$400).

VI. BIOSTATISTICAL ANALYSIS

Sample size: Based on previous data from the study of the noradrenergic drug desipramine in OSA patients, 20 patients will enable us to detect a reduction in AHI of $50\pm75\%$ (80% power, alpha 0.05), primary outcome. 20 patients will also enable us to detect a $100\pm150\%$ increase in genioglossus activity (80% power, alpha 0.05), secondary outcome. Accounting for a 20-50% failure rate of these kind of physiology studies we anticipate that we may need to enroll up to 30 patients to conclude the study

Variables of interest will be compared using a Wilcoxon matched-pairs signed rank test, with a p-value <0.05 considered statistically significant. To compare the effect of placebo, ato-oxy, atomoxetine alone and oxybutynin alone in the participants who will perform 4 study nights, we will use the Friedman's test with a post-hoc analysis (Wilcoxon) in which each treatment will be compared to placebo; the post-hoc analysis will be conducted with Bonferroni correction (p-threshold=0.017).

VII. RISKS AND DISCOMFORTS

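### The single-drug nights always follow the placebo and combination nights, so the four-night Friedman test and the two single-drug contrasts with placebo confound drug with night order

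*Combined protocol and SAP*

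**What the plan says.** - **Section IV (Subject Enrollment)** puts the single-drug nights after the main study. Once that is complete, "patients enrolled will be asked to perform two extra study nights in which atomoxetine and oxybutynin alone will be administered". The invitation depends on improvement in genioglossus activity and OSA severity "in the night in which they took the combined therapy". No order, randomisation, participant blinding, spacing or further placebo night is given for these extra nights.
- **Section V (Study Procedures, Protocol)** describes the main study: "Two overnight sleep studies will be performed approximately 1 week apart", one on placebo and one on ato-oxy, "in double-blinded randomized control design". That phrase covers those two nights only.
- **Section V (Data Analysis)** says that sleep and respiratory events are scored by a technologist who does not know the allocation.
- **Section VI (Biostatistical Analysis)** takes the participants with four nights, applies Friedman's test to the four treatments, and follows it with Wilcoxon tests "in which each treatment will be compared to placebo", Bonferroni-corrected to 0.017. It includes no period or order term and no caveat about the later nights.

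**The concern.** Friedman's test assumes that, if treatment does nothing, a patient's four nights are exchangeable. Randomising the order would secure that; this design does not. Placebo and ato-oxy share positions 1 and 2, and the single drugs share positions 3 and 4.

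A night effect is plausible here. Patients sleep with a nasal pressure catheter and, in some cases, wires in the tongue, and the protocol's own risk section accepts that the electrodes may disturb sleep. Patients may adapt over successive nights, and the gap before the extra nights is open-ended. A drift towards lower AHI would be credited to atomoxetine or oxybutynin alone; a drift the other way would hide a real effect. These nights are the plan's only evidence on whether either drug works by itself.

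The point is separate from the selection of patients who improved on the combination. It would remain if every completer were invited.

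**Working it through.** **The plan's own figures.** Three contrasts with placebo at an overall 0.05 give 0.05/3 = 0.0167, which is the stated 0.017. The stated 20 patients for a 50% reduction with SD 75% also reproduces: the standardised effect is 50/75 = 0.667, and a two-sided paired t-test at 0.05 with n = 20 has power 0.807. That sample size belongs to the two-night comparison.

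**What each contrast estimates.** Let E be the mean effect of being on night 1 or 2, and L that of being on night 3 or 4.

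- Ato-oxy minus placebo = drug effect + (E − E) = drug effect. The order is randomised within the pair.
- Atomoxetine minus placebo = drug effect + (L − E).
- Oxybutynin minus placebo = drug effect + (L − E).

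The omnibus test and two of the three post-hoc contrasts therefore carry L − E. The Bonferroni threshold allows for the number of tests and does nothing about this term.

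**Size, under assumptions.** The simulation has four nights per patient with equal variance, the SD of a paired difference set to 1, no drug effect, and nights 3-4 shifted in the favourable direction. Friedman is tested at 0.05. The signed-rank test is two-sided at 0.017, counting only results that favour the drug (nominal about 0.8%). On the plan's SD of 75 points, 0.1, 0.3 and 0.5 SD are 7.5, 22.5 and 37.5 percentage points. The number of four-night patients is not stated; n = 15 is assumed.

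| Late-night shift | Friedman rejects | Each single drug falsely better | Same, only if Friedman is significant |
|---|---|---|---|
| 0.1 SD | about 5% (5-6% across runs) | about 2% | about 1% |
| 0.3 SD | about 18% | about 8% | about 5% |
| 0.5 SD | about 45% | 22-24% | about 18-19% |

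At 0.3 SD, n = 10 gives 12% (Friedman) and 4.6% (each single drug); n = 20 gives 24% and 11%. Ato-oxy against placebo stays at its nominal rate throughout.

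**Check that order is the cause.** With all four nights in random order, n = 20 and a 0.5 SD shift, Friedman rejects in 5% and each contrast (two-sided) in 1.0-1.7%. With the single-drug nights fixed last, the same shift gives about 60% and 34%.

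**Would a night-number term help?** Placebo never falls on nights 3-4 and no single drug falls on nights 1-2. With night as a factor, the single-drug contrasts with placebo cannot be estimated. With night as a linear trend, they rest on extrapolating from nights 1-2.

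**The case against.** The strongest reply is that this analysis is peripheral. The specific aim in section II concerns the combination. The sample size and the primary and secondary outcomes in section VI rest on two nights, and the four-night analysis has no stated sample size or hypothesis and is nowhere called confirmatory. That stands, and it limits the weight of the point. Even so, an omnibus test followed by multiplicity-adjusted contrasts invites an inferential reading, and the plan gives no warning against one.

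The error rates also depend on a drift that the documents do not quantify. This too stands. A shift of 0.3 SD is 22.5 points, nearly half of the 50% effect the trial is sized for, and a shift of 0.1 SD barely moves Friedman. If the post-hoc tests are read only after a significant Friedman test, which is the usual practice but is not spelled out, the single-drug rates fall as tabulated. The non-separability needs none of these assumptions.

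Blinded scoring limits assessment bias on AHI. It does not remove an effect of night order.

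A reader might infer that the primary result, or every contrast with placebo, is compromised, or that 0.017 should be abandoned. The documents do not support this: ato-oxy and placebo are randomised against each other, and 0.017 is a correct allowance for three tests. A reader might also infer that the extra nights are open-label or given in a fixed order. The documents are silent on both, and silence does not establish either.

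**Conclusion.** The concern holds for three analyses: the four-treatment Friedman test, atomoxetine against placebo, and oxybutynin against placebo. In each, a drug effect cannot be told from a late-night effect, and this follows from the schedule alone.

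The primary two-night comparison is unaffected, and the ato-oxy post-hoc contrast is free of order confounding. (Whether selecting improvers biases that contrast is a different question.)

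The consequence runs from negligible at 0.1 SD to serious at 0.5 SD. Those figures assume the shift, its favourable direction, n = 15 and no drug effect, so they illustrate sensitivity and do not estimate this trial's error rate. The point merits a change to the plan but does not threaten the main conclusion.

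**What to change.** 1. In sections IV and V, randomise the order of the two extra nights and state that they are double-blind. In section VI, add atomoxetine against oxybutynin as the randomised contrast within those nights.
2. In section VI, state that the four-night Friedman test and the two single-drug contrasts with placebo are exploratory, non-randomised and confounded with night order. The 0.017 threshold can stay as a multiplicity allowance, provided it is not presented as protection against order effects.
3. Do not rely on a night-number term to remove the confounding.

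The cost is protocol and SAP wording and a second randomisation list. The downside is that claims about either drug alone against placebo become exploratory. If a randomised claim of that kind is wanted, the first step is not enough, because it protects only the comparison between the two single drugs. The extra phase would need its own placebo night in the random order, at the cost of another instrumented night per patient. Alternatively, all four nights would have to be randomised from the start, which cannot be combined with inviting patients on the strength of their combination night.

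### On the most natural reading of the entry rule, the four-night ato-oxy versus placebo AHI test reflects only the number of entrants

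*Combined protocol and SAP*

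**What the plan says.** The main study has two nights per patient (section V, Protocol): "Two overnight sleep studies will be performed approximately 1 week apart: a placebo night and a Atomoxetine-Oxybutynin" night, randomised and double-blind. The last paragraph of section IV adds two further nights, one on each drug alone, for patients "if they showed an improvement in EMG_{GG} activity and OSA severity in the night in which they took the combined therapy". It does not say what the improvement is measured against, which measure of severity or muscle activity counts, or whether the rule is applied to each patient or to the group.

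Section VI plans a separate analysis, with this purpose: "To compare the effect of placebo, ato-oxy, atomoxetine alone and oxybutynin alone in the participants who will perform 4 study nights". The method is a Friedman test, followed by Wilcoxon tests that set ato-oxy and both single drugs against placebo in turn. The post-hoc tests are Bonferroni-corrected, with a threshold of 0.017. No placebo or ato-oxy night is repeated for this analysis. The plan gives no caveat about how these participants were chosen, no expected number of them, and no exploratory label.

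**The concern.** Entry to the four-night set depends on how a patient did on the ato-oxy night, and the set is then used to test ato-oxy against placebo on the main-study nights. If entry required a lower AHI on ato-oxy than on placebo, the test asks a question that the entry rule has already answered. Its error rate would not be 0.017, and its result would say nothing about the size of the effect.

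Two misuses are possible. A two-night comparison that shows no effect could be offset by a formally significant result in the subset. Or the subset result could be read as independent evidence when it comes from the same two nights in patients picked for a favourable difference.

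**Working it through.** **Inputs from the plan**
- Threshold: three comparisons with placebo, 0.05/3 = 0.0167, which reproduces the stated 0.017.
- Nights: two main plus two extra make four. Section V (Reimbursement) agrees: 400 dollars at 100 per night is four nights. The placebo and ato-oxy nights in the four-night set are therefore those of the main study.
- Completers: section VI plans on 20 for an AHI reduction of 50% with SD 75%. The paired normal formula gives (75 × (1.960 + 0.842)/50)² = 17.66, so 18, and a paired t test with 20 has 80.7% power, so the figure of 20 is sound. Enrolling 30 with the stated 20-50% failure rate leaves 30 × 0.5 = 15 to 30 × 0.8 = 24.

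**Assumptions not in the plan**
- The rule is applied to each patient, against the placebo night, using the same AHI measure that is later tested.
- All eligible patients accept, unless stated otherwise.
- The test is exact and two-sided; section VI specifies neither.
- The correlation between AHI and EMG_GG improvement is 0 or 0.5.

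**Step 1: p when every difference has the same sign.** The signed-rank statistic is then at its extreme, and the exact two-sided p is 2/2^n:
- n = 6: 2/64 = 0.031, above 0.017
- n = 7: 2/128 = 0.0156, below 0.017
- n = 8: 2/256 = 0.0078

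The size of the differences plays no part. The cut-off moves with the version of the test. The normal approximation at n = 7 has mean 14 and SD √35 = 5.92, so z = 2.37 and p = 0.0180; at n = 8, p = 0.0117. That version needs 8 entrants. A one-sided exact test needs 6 (1/64 = 0.0156).

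**Step 2: how often enough patients enter when ato-oxy has no average effect.** For two normal changes with correlation r, P(both improve) = 1/4 + arcsin(r)/(2π), which is 0.25 at r = 0 and 0.333 at r = 0.5. The rejection rate is the binomial probability of reaching the cut-off:

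| Case | r = 0 | r = 0.5 |
|---|---|---|
| 20 completers, cut-off 7 | 0.214 | 0.521 |
| 15 completers, cut-off 7 | 0.057 | 0.203 |
| 24 completers, cut-off 7 | 0.393 | 0.737 |
| 20 completers, 75% uptake, cut-off 7 | 0.065 | 0.214 |
| 20 completers, 50% uptake, cut-off 7 | 0.008 | 0.037 |
| 20 completers, normal approximation, cut-off 8 | 0.102 | 0.339 |
| 20 completers, one-sided, cut-off 6 | 0.383 | 0.703 |

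The nominal level is 0.017.

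**Step 3: requiring a significant Friedman test first.** Simulation with 20 completers and no drug effect gives about 10-13% (r = 0) or 32-38% (r = 0.5). The Friedman test includes the selected nights too: it passes 0.05 in 27-43% or 51-70% of such trials.

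**Step 4: other readings of the rule, same null, 20 completers (simulation)**
- Severity judged against the entry AHI (section III): 2-8% or 9-27%. The test is biased, but the signs are not fixed.
- Group-level trigger: 1-2%, so no problem.

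**Step 5: the single drugs.** The reused placebo night was selected to look bad. At the planned ato-oxy effect, an inert single drug shows an apparent AHI reduction of about 4 to 19 percentage points if 25-100% of the variance is night-to-night noise, a share the plan does not give. The chance that at least one inert single drug passes 0.017 is 4-10%, against about 3% without selection. If ato-oxy is inert too, it is 1-3% (r = 0) or 3-8% (r = 0.5).

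**The case against.** **The reading is not the only one.** This stands. A reader might infer that the four-night result is always set by the number of entrants. The documents support that only for a patient-level rule judged against the placebo night by AHI. The patient-level reading is the more natural, because section VI speaks of those participants who perform four nights, but section IV does not settle it.

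**The Friedman test may come first.** Section VI does not state this as a condition, but post-hoc tests are commonly read that way. If so, 7 entrants do not guarantee a significant result, and the lower rates in step 3 apply.

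**It would not falsely confirm the primary result.** This also stands. With no average effect, the two-night test favours ato-oxy in only about 2.5% of trials, and both tests do so in about 1.4-2.5%. The realistic error is the reverse: a significant subset beside an unconvincing primary, in at least 21.4 - 2.5 = 18.9% (r = 0) or 52.1 - 2.5 = 49.6% (r = 0.5) of null trials in the base case. At the planned effect the four-night test rejects in 98% or more of trials, but that is a correct rejection and not an error rate.

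**EMG_GG.** One might infer that the muscle-activity re-test is fixed as well. It need not be. Section V records quiet wakefulness on each night, so improvement could be judged within the night. Its Data Analysis part also lists several measures: peak phasic and tonic activity, by sleep state, and the slope and intercept against pressure. Only the measure used for selection is fixed, and only if it is compared with the placebo night.

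**Reach.** The specific aim in section II concerns the combination, and the four-night set is neither the primary nor the secondary outcome. That limits the importance, but section VI still gives the test a formal threshold.

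**Conclusion.** The concern holds conditionally and is worth fixing. If improvement is judged patient by patient, against the placebo night and by AHI, the post-hoc AHI test of ato-oxy against placebo depends only on how many patients enter. Its false-positive rate with 20 completers and full uptake is then about 21% or 52% instead of 1.7%, or about 10-13% or 32-38% behind a significant Friedman test. These figures rest on the assumed correlation, and lower uptake reduces them, to 0.8% or 3.7% at 50% uptake; even then p reflects only the entrant count. Under the entry-AHI reading the bias is smaller, and under a group-level rule there is none.

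Two stronger conclusions are not supported. The main result is not compromised: the two-night primary and secondary comparisons precede the selection. Nor are the single-drug comparisons invalid: their bias is small, depends on an unknown noise share, and can leave the error rate below the unselected 3%.

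**What to change.** **Section VI**
- Remove ato-oxy versus placebo from the four-night post-hoc tests and report it there descriptively. Take that contrast only from all participants with both main nights.
- Test each single drug against placebo with Bonferroni over two comparisons (0.05/2 = 0.025), or keep 0.017 as the conservative choice. The single-drug error rates above were computed at 0.017.
- Label the four-night set, including its Friedman test, as responder-selected and exploratory. Note regression to the mean and night order: the single-drug nights always follow the main nights, and randomisation and double-blinding are stated only for the latter.

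**Section IV**
- State the reference night and the measure for improvement, for both OSA severity and EMG_GG, and whether the rule applies to each patient.

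**Cost.** Wording only, with no added nights or patients. The four-night set loses one formal test.

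### If responders are picked against the placebo night, reusing that night as the single-drug comparator makes an inert component look effective

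*Combined protocol and SAP*

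**What the plan says.** Section V (Protocol) sets out the main study: "Two overnight sleep studies will be performed approximately 1 week apart: a placebo night and a Atomoxetine-Oxybutynin" night, randomised and double-blind.

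Section IV adds a second stage. After the main study, "patients enrolled will be asked to perform two extra study nights in which atomoxetine and oxybutynin alone will be administered", but only "if they showed an improvement in EMG_{GG} activity and OSA severity in the night in which they took the combined therapy". It gives no threshold for improvement and does not say which recording the combination night is compared with.

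Section VI analyses this subset as a four-condition set: "To compare the effect of placebo, ato-oxy, atomoxetine alone and oxybutynin alone in the participants who will perform 4 study nights", a Friedman test is followed by a "post-hoc analysis (Wilcoxon) in which each treatment will be compared to placebo"; "the post-hoc analysis will be conducted with Bonferroni correction (p-threshold=0.017").

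The count of nights shows that placebo is not repeated. Two main-study nights plus one night for each single drug make four. The Reimbursement paragraph of Section V agrees: "they will be paid \$100/night (total \$400"), that is 4 × $100. The placebo value in the subset analysis is therefore the main-study placebo night.

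**The concern.** Suppose a patient qualifies because AHI on the combination night was lower than on the placebo night. That can happen because the combination worked, because the combination night was good by chance, or because the placebo night was bad by chance. Selection on the difference draws in all three. Among those invited, the placebo night therefore overstates the patient's usual AHI on average. If EMG_GG is judged the same way, it understates usual muscle activity.

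The single-drug nights come later and play no part in the selection, so they fall back towards the patient's usual level. When each is compared with the selected placebo night, even an inert drug shows a lower AHI. Randomising or blinding the extra nights would not prevent this. Bonferroni correction deals with the number of tests and does nothing about a biased reference.

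These nights are the plan's only data on each component by itself. The risk is that an inactive component is credited with an effect.

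**Working it through.** **Inputs from Section VI.** AHI reduction 50±75%; EMG_GG increase 100±150%; 20 patients; 80% power; alpha 0.05; post-hoc threshold 0.017. I read ± as the SD of the paired change and alpha as two-sided.

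**The plan's own figures.** The standardised effect is d = 50/75 = 0.667, and 100/150 gives the same. A paired t calculation (noncentral t) needs 20 patients, with power 0.807 at n = 20, so the sample size reproduces. The threshold is 0.05/3 = 0.0167. A false positive in the drug's favour should therefore occur in 0.0167/2 = 0.83% of trials.

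**How many are invited.** If any improvement counts, P(AHI improves) = Φ(0.667) = 0.7475. With EMG_GG independent and at the same d, both improve with probability 0.7475² = 0.559, so 20 × 0.559 ≈ 11 patients.

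**Size of the bias.** Let f be the share of the paired variance (75²) that is noise in the placebo night. The combination night has the same share, and the remaining 1 − 2f is true variation in response. Let D be placebo minus combination, with mean 50 and SD 75, and keep the patient if D > 0. The covariance of the placebo-night noise with D is f × 75². Hence

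expected placebo excess = f × 75 × φ(d)/Φ(d) = f × 75 × 0.3194/0.7475 = f × 32.05.

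An inert single-drug night has no such excess, so this is the false benefit. The table adds the rate at which an inert drug is declared better in simulation: 20 completers, both criteria required, AHI and EMG_GG independent, signed-rank test at 0.05/3. The ranges cover repeat runs.

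| Noise as share of paired variance (2f) | f | False AHI reduction (points) | Inert drug declared better |
|---|---|---|---|
| Quarter | 0.125 | 4.0 | 1.6-1.8% |
| Half | 0.25 | 8.0 | 2.1-2.2% |
| All | 0.5 | 16.0 | 2.7-3.8% |

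Points are percent of a typical AHI. Requiring the Friedman test to be significant first did not change these figures.

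**Sensitivity.**
- If AHI and EMG_GG noise correlate at 0.5, the half and all cases become 10.7 and 18.7 points.
- If the combination is stronger (75±75%, d = 1), the multiplier is 75 × 0.2420/0.8413 = 21.6, giving 2.7, 5.4 and 10.8 points.
- If the combination has no mean effect (d = 0), the multiplier is 75 × 0.3989/0.5 = 59.8, giving 7.5, 15.0 and 29.9 points under AHI selection.

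**Check of the remedy.** With all completers invited regardless of response (f = 0.25), the false benefit is 0.1 points and the error rate 0.8%.

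**The case against.** The strongest objection is that the premise is inferred. Section IV does not say the combination night must beat the placebo night. If OSA improvement were judged against an earlier diagnostic study, the bias through the placebo night would largely disappear. Such a value should exist, because Section III requires an AHI above 10 in supine NREM sleep. A reader might also infer that EMG_GG can be judged only against placebo. That is too strong: Section V records at least 15 minutes of quiet-wake EMG_GG each night, so a sleep-to-wake comparison within the combination night is possible. This objection stands to the extent that the point must be conditional. The placebo night remains the natural reading, and the silence needs correcting either way.

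The size is also uncertain. Sixteen points requires every patient to have the same true response. The documents give no night-to-night variance and recruit a wide AHI range. The normal model is rough too, since a mean of −50% with SD 75% puts Φ(−0.667) = 25% of patients below −100%, which is impossible. The figures are a guide to scale.

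A reader might infer a higher false-positive rate by assuming 30 completers. Section VI has up to 30 enrolled with 20-50% failure, which leaves 30 × 0.5 = 15 to 30 × 0.8 = 24.

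Finally, the Specific Aims name only the combination, and the single-drug nights are an add-on. Studying components in responders is a defensible choice. That lowers the importance of the point but does not make the reused comparator unbiased.

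**Conclusion.** The point holds conditionally. If improvement is judged against the randomised placebo night, both single-drug contrasts with placebo are biased in the drug's favour. At the planned effect and with 20 completers, the bias is about 4, 8 or 16 points for a noise share of a quarter, half or all of the paired variance. The share is an assumption. Sixteen is the ceiling over that share when AHI and EMG_GG noise are independent; correlated noise or a weaker combination raises the figures, and a stronger combination lowers them. In the all-noise case the bias is 16/50, about a third of the planned effect.

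The error rate rises from 0.83% to about 2-4%. That stays below 5% per contrast, so the distorted estimate is the main problem and the test is a lesser one.

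A reader might infer that the trial's main result is compromised. The documents do not support that: the primary two-night comparison uses all patients and involves no selection on response. Nor do they show any intent to favour a component, since no hypothesis about either drug alone is stated. This is a weakness in a secondary analysis that is worth correcting.

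**What to change.** In Section IV, invite consecutive completers to the single-drug nights regardless of their response, until a stated number of four-night sets is reached. The plan gives no such number; the present rule would yield about 11 from 20 completers. The change is one sentence and adds no study nights. The small downside is that some of those invited will not have responded to the combination, so the subset no longer describes responders only.

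If the sponsor keeps responder selection, Section IV should say that improvement is judged against a pre-study AHI and not the placebo night. In simulation, with EMG_GG dropped from the rule, this brings the bias within ±0.1 points and the error rate to 0.7-1.1%. It depends on a comparable recording being available. The documents do not establish that: patients may come from an existing database, the entry AHI is for supine NREM only, and no pre-study sleep EMG_GG is planned.

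If neither is done, Section VI should state that single-drug versus placebo estimates in the subset are biased in favour of the drug, and that no efficacy conclusion will be drawn from the 0.017 tests. Dropping the tests alone would not be enough, because the estimates would still be biased.
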